10.8.2 ORR

The ORR observed in the treatment groups will be compared adjusting for the stratification variables using the Cochran-Mantel-Haenszel (CMH) test using PROC FREQ in SAS. A 95% CI will be calculated by treatment arm for the true ORR.

Example of PROC FREQ for testing ORR is provided below:

```
proc freq data=<ORR>;
  tables <trt> * <Response> / relrisk cmh;
  weight Count;
run;
```

The best overall response outcome (CR/PR/SD/PD/NE) will be summarized and tabulated for the FAS by treatment group.

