For such patients, the progression or censoring date will be determined based on described conventions ([FDA 2007](#)). Sensitivity analyses will be performed to assess the impact of the different censoring mechanisms and deviations from the planned schedule of disease assessments ([Bhattacharya 2009; Stone 2011](#)).

ORR will be estimated based on the crude proportion of patients in each treatment arm whose best overall response during the course of study treatment is CR or PR. Tumor response will be assessed using irRECIST. Approximate 95% confidence intervals will be calculated by treatment arm for the true ORR. The inferential comparison of the observed ORRs will be made using the Cochran-Mantel-Haenszel chi-square test, stratified by the randomization stratification factors. The corresponding results without stratification will be reported as supplemental analyses.

DOOR will be calculated for patients who achieve CR or PR. For such patients, DOOR is defined as the number of months from the start date of PR or CR (whichever response occurs first) and subsequently confirmed, to the first date that recurrent or progressive disease is documented. The date of progression or censoring for DOOR will be determined using the conventions described for PFS. DOOR will be summarized descriptively for each treatment arm using the Kaplan-Meier method. Inferential comparisons between treatment arms for DOOR are not planned.

CBR will be estimated based on the crude proportion of patients in each treatment arm whose best overall response during the course of study treatment is CR, PR, or stable disease lasting for at least 24 weeks. Stable disease will be measured from the start date of study treatment until the criteria for progressive disease is first met. The analysis of CBR and its duration will be based on the methods described above for ORR and DOOR, respectively.

OS is defined as the number of months from randomization to the date of death (due to any cause). Patients who are alive or lost to follow-up as of a data analysis cutoff date will be right-censored. The censoring date will be determined from the patients' date of last contact or data analysis cutoff date, whichever date occurs first. The analysis of OS will be based on the methods described above for PFS.

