5.3 Randomization and Stratification

The randomization technique used for the study is a stochastic minimization, using minimization probability parameter of 0.80. The randomization is performed via ID-net (which is the IWRS from IDDI).

Prior to dosing, eligible patients are randomized in a 1:1 ratio into 2 treatment arms, stratified by geographic location.

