10.8.1 PFS

The duration of PFS will be summarized descriptively using Kaplan-Meier (KM) curves. Inferential comparisons between treatment arms will be made using stratified log-rank test, stratifying on

**Statistical Analysis Plan
SNDX-275-0602 (TRIO025)
DM-025-037**

geographic location (US vs. Rest of World). The KM estimate of the PFS survival distribution function will be computed for each treatment group using PROC LIFETEST with method=KM option in SAS. For each treatment group, the KM estimates for the median PFS time, the first and third quartiles will be presented, along with approximate 95% confidence intervals (CI) calculated using Greenwood's formula. Example of PROC LIFETEST code with and without stratification is presented below:

```
* Unstratified;
proc lifetest data=<PFS> method=km;
  time <pfsmmonth*<pfscens>(1);
  strata <trt>;
run;

* Stratified;
proc lifetest data=<PFS> method=km;
  time <pfsmmonth*<pfscens>(1);
  strata <geographical region> / group= <trt>;
run;
```

The effect of treatment on PFS will also be compared using a stratified Cox proportional hazards model. The hazard ratio with two-sided 95% CI will be derived from the stratified Cox proportional hazards model using PROC PHREG with ties=EXACT option in the model. Homogeneity in the hazard ratios between randomization strata will be examined by Wald's test. The corresponding results without stratification will be reported as supplemental analyses.

Example of PROC PHREG code with and without stratification is presented below:

```
* Unstratified;
proc phreg data=PFS;
class trt(ref='1');
model dfsmmonth*dfscens(1)=trt / risklimits ties=exact;
run;

* Stratified;
proc phreg data=PFS;
class trt(ref='1');
model dfsmmonth*dfscens(1)=trt / risklimits ties=exact;
strata <geographical region>;
run;
```

Testing of Proportional Hazard assumption will also be done using the following stratified model:

```
proc phreg data=pfs;
  model <pfsmmonths*<pfscens>(1)= <trt> / risklimits Ties=exact;
    assess var=(<trt>) ph / crpanel resample seed=199;
    strata <geographical region>;
run;
```

**Statistical Analysis Plan
SNDX-275-0602 (TRIO025)
DM-025-037**

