10.8.3 CBR

The analysis of CBR will be based on the methods described above for ORR.

10.8.4 OS

The analysis of OS will be based on methods described above for PFS.

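### The only example code for ORR (and, by reference, CBR) in SAP 10.8.2 leaves out region, so it runs the unstratified test instead of the stratified CMH test that the text specifies

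*SAP*

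**What the plan says.** - **SAP 10.8.2, text.** ORR is to be "compared adjusting for the stratification variables using the Cochran-Mantel-Haenszel (CMH) test". The randomization has one stratification factor, geographic location (US vs rest of world; protocol 6.1, SAP 3.2).
- **SAP 10.8.2, code.** The block is introduced with "Example of PROC FREQ for testing ORR is provided below". Its TABLES request is "tables <trt> * <Response> / relrisk cmh", followed by `weight Count;`. No stratified version follows, and the block is not labelled unstratified or supplemental.
- **Protocol 13.5.5.** The ORR comparison is the "Cochran-Mantel-Haenszel chi-square test, stratified by the randomization stratification factors". It adds: "The corresponding results without stratification will be reported as supplemental analyses".
- **SAP 10.8.3.** "The analysis of CBR will be based on the methods described above for ORR".
- **SAP 10.8.1, for contrast.** For PFS the SAP states "Example of PROC LIFETEST code with and without stratification is presented below". It labels each block and names the region variable in the stratified one.

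**The concern.** In PROC FREQ the CMH option adjusts only for variables placed ahead of the last two in the TABLES request. A request with arm and response alone has one stratum, so its CMH statistic is not adjusted for anything. The code placed directly under the sentence specifying the stratified test therefore delivers the analysis that the protocol makes supplemental.

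If that block becomes the programming template, the main ORR and CBR comparisons, under both RECIST 1.1 and irRECIST, would duplicate the supplemental analysis and the specified one would not be produced. Text and code in one SAP section would give different p-values, with nothing in the documents to say which prevails. SAP 10.8.2 does not mention an unstratified ORR analysis at all, so a reader of the SAP has no cue that the code shown is the supplemental form. The `weight Count;` line implies cell-count input; if those counts were built by arm and response only, region could not be recovered later.

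**Working it through.** The documents give no numerical result for the ORR or CBR test, so there is no stated figure to reproduce. The check has three parts.

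**1. What the code computes.** Over strata, the Mantel-Haenszel statistic is

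Q = [Σ(a − E)]² / ΣV, with E = n₁m/N and V = n₁n₀m(N − m) / [N²(N − 1)],

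where a is the number of responders on entinostat, n₁ and n₀ are the arm sizes, m is total responders and N is total patients in the stratum. With one stratum, Q equals Pearson chi-square × (N − 1)/N. Illustration, 10/35 vs 4/35:
- E = 35 × 14/70 = 7, so a − E = 3.
- V = 35 × 35 × 14 × 56 / (70² × 69) = 2.841.
- Q = 9/2.841 = 3.168.
- Pearson = 70 × (10 × 31 − 25 × 4)² / (35 × 35 × 14 × 56) = 3.214, and 3.214 × 69/70 = 3.168.

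The two-way request is thus a lightly rescaled Pearson test.

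**2. A worked contrast** (hand-picked, arms nearly balanced within region). Responders are 7/17 vs 4/18 in one region and 1/18 vs 0/17 in the other.

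| | a − E | V |
|---|---|---|
| Region A: m = 11, N = 35 | 7 − 17 × 11/35 = 1.657 | 17 × 18 × 11 × 24 / (35² × 34) = 1.940 |
| Region B: m = 1, N = 35 | 1 − 18/35 = 0.486 | 18 × 17 × 1 × 34 / (35² × 34) = 0.250 |
| Stratified sum | 2.143 | 2.189 |
| Collapsed, 8/35 vs 4/35 | 8 − 6 = 2 | 35 × 35 × 12 × 58 / (70² × 69) = 2.522 |

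Stratified: z = 2.143/√2.189 = 1.448, one-sided p = 0.074. Code as written: z = 2/√2.522 = 1.259, p = 0.104. These fall on opposite sides of the one-sided 0.1 level in protocol 13.5.5.

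The difference can also go the other way. With 3/22 vs 2/26 and 7/13 vs 3/9, the code as written gives 0.074 and the stratified test 0.128. That table needs an arm imbalance of 4 in both regions, which is about the 99th percentile of the larger within-region imbalance under the allocation rule simulated below.

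**3. How often it would matter.** Each scenario had 40,000 simulated trials of 70 patients. Allocation was a 0.8 biased coin within region, which is what "a stochastic minimization, using minimization probability parameter of 0.80" in SAP 5.3 reduces to with a single factor. Both statistics were computed on the same data and compared with z > 1.2816 (one-sided 0.1 applied to the signed root of Q). The US share, the regional rates and the response ratio of 1.6 are assumptions. The documents give only an 18–19% response rate in PD-L1-positive TNBC (protocol 5.2).

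| Control ORR by region (US share 30%, 50% or 70%) | Verdict differs | Median p-difference |
|---|---|---|
| 18% in both | 0.6% | 0.001–0.002 |
| 10% vs 25% | 1.9–2.2% | 0.004–0.005 |
| 5% vs 30% | 3.8–5.4% | 0.009–0.015 |

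| CBR-like control rate by region (US share 50%) | Verdict differs |
|---|---|
| 30% in both | 0.5% |
| 20% vs 40% | 3.0% |
| 15% vs 45% | 6.2% |

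With no treatment effect at the ORR rates, the stratified test rejects in 9.9–10.3% of trials and the code as written in 8.7–9.9%. At 5% vs 30%, power falls from about 51% to 48%, 44% to 40% and 37% to 31% for US shares of 30%, 50% and 70%.

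**The case against.** The strongest reply is that no analysis choice is wrong. Both documents state the stratified test, and the snippet is labelled an example. It uses placeholders and an undefined `Count` variable, so someone must adapt it before it runs. The neighbouring PFS examples are not production code either: one PFS model uses variable names beginning with dfs. SAP 9.1 and 9.6 require review of outputs, datasets and programs, which could catch a missing stratum. The endpoints are secondary, the larger effects need sharp regional contrasts that no section supports, and the error runs in the conservative direction.

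All of this stands as to weight. It does not remove the mismatch. The code is presented as the code for testing ORR, directly under the sentence specifying the stratified test. In 10.8.1 the region variable is written out and each block labelled, so its omission here is not a placeholder convention. A checker comparing the program with the SAP's own example could pass the wrong test. Under SAP 9.2 the unblinded run is done by a statistician who does not work on the study directly, which makes literal use somewhat more likely. The point about `weight Count;` is conditional: nothing says how the counts are built.

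**Conclusion.** The concern holds. As written, the SAP's only ORR code performs the unstratified test, contrary to the SAP text above it and to protocol 13.5.5, and CBR inherits the gap. That a two-way request is treated as one stratum is standard software behaviour; the documents do not state it.

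The practical effect is small. The verdict changes in roughly 0.5% of trials when regions respond alike, rising to about 6% under the strongest regional contrast assumed, with a modest loss of power and no inflation of type I error in the ORR scenarios tested. These figures depend on the assumed US share, regional rates and response ratio. The main reason to act is that the pre-specified ORR and CBR result should be unambiguous before unblinding.

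**What to change.** In SAP 10.8.2, give this request for the main comparison:

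`tables <geographical region> * <trt> * <Response> / relrisk cmh;`

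If a cell-count dataset is used, build `Count` by region, arm and response. Keep the present two-way request and label it as the supplemental unstratified analysis, following the labelling in 10.8.1. State that both forms apply to CBR through 10.8.3.

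The cost is one added line of code and two labels. The stated method, data collection and sample size do not change.

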10.8.3 CBR

The analysis of CBR will be based on the methods described above for ORR.

10.8.4 OS

The analysis of OS will be based on methods described above for PFS.

10.8.5 DOR and TTR

DOR and TTR will be summarized descriptively for each treatment arm using the KM method. Inferential comparisons between treatment arms for DOR and TTR are not planned.

**Statistical Analysis Plan
SNDX-275-0602 (TRIO025)
DM-025-037**

10.8.6 Anticancer therapy after end of study treatment

A summary of number of patients received anticancer therapy after end of study treatment will be tabulated by the type of therapy according to treatment group.

10.9 Safety Analyses

Safety analyses will be performed on the safety analysis set.

10.9.1 Physical Examinations

The number of patients who had done complete and/or symptom-directed physical examinations at each visit will be tabulated by treatment group.

10.9.2 Adverse Events

The reported AE term will be coded using the current version of the MedDRA. The severity of AE will be presented as reported by the investigator based on NCI CTCAE version 4.03.

Incidence of TEAE will be tabulated by SOC, PT for:

- All TEAEs
- TEAEs by relationship to study treatment and maximum severity grade
- TEAEs with action of study treatment delayed/interrupted or dose reduced
- TEAEs with action of study treatment discontinued
- Serious Adverse Events (SAE) (not Serious TEAEs)

In the event a patient experiences repeat episodes of the same AE, the event with the highest severity grade and strongest causal relationship to study treatment will be used for purposes of incidence tabulations.

All AEs leading to deaths will be summarized (not TEAEs). An AE will be considered as leading to death if it has a grade 5.

Detailed listings for all AEs will be provided. A flag will be used to identify which AE is considered as treatment emergent.

For the Phase 1b dose determination phase, the observed DLT rate in each dose cohort will be calculated by the crude proportion of patients who experienced DLT with a 2-sided 95% exact binomial CI.

**Statistical Analysis Plan
SNDX-275-0602 (TRIO025)
DM-025-037**

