13.1.2 Expansion Phase

The Expansion Phase will evaluate the efficacy and safety of entinostat when administered at the recommended Phase 2 dose with atezolizumab in a randomized, double-blind, placebo-controlled setting. Up to 70 eligible patients with metastatic TNBC will be randomized to receive atezolizumab with entinostat or placebo in a 1:1 allocation.

The true median PFS for patients with aTNBC receiving atezolizumab monotherapy is expected to be approximately 4 months from the initiation of such treatment. It is hypothesized that the combination of entinostat and atezolizumab will improve true median PFS by 3 months (i.e., from 4 to 7 months). Under the exponential distribution, such an improvement in median PFS represents a reduction of 43% for the true PFS failure hazard rate or equivalently, a hazard ratio of 0.57. Inferential comparisons will be performed using a stratified log-rank test, stratifying on the randomization stratification factor of geographic location. Total information of 60 PFS failures, defined as documented progressive disease by RECIST 1.1 or death due to any cause

without documented progressive disease beforehand, is estimated to provide 80% power to detect a 43% reduction in the PFS failure hazard rate with 1-sided significance level of 0.1 (SEQDESIGN procedure, SAS version 9.2).

Assuming approximately 9 months of accrual and an additional 9 months of follow-up, total accrual of 70 patients (approximately 35 per treatment arm) is projected to result in 60 PFS failures within approximately 18 months of the first patient randomization. Patients who discontinue study treatment for reasons not due to documented progressive disease by RECIST 1.1 will continue to undergo disease assessments until the earlier of documented progressive disease, death, or withdrawal of consent/lost to follow-up. It is anticipated that the number of patients who will drop out of the study without PFS failure beforehand will be low (2–3%). Depending on the actual number of such dropouts, the number of patients accrued may be increased by 6–10 additional patients to accommodate for a higher-than-expected number of dropouts.

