13.2 Phase 2 Interim Efficacy Analyses

The sample size and number of PFS failures were adjusted using the O'Brien -Fleming group sequential procedure to account for 1 planned interim analysis of PFS after 45 events (75% information). It is projected that 75% and 100% of total information will be reported at approximately 12 and 18 months, respectively.

The interim analysis will be performed to support the Sponsor's product development plans and ongoing resourcing activities. Although there are no plans to terminate the study early because of early evidence of superior efficacy for the combination treatment, the significance levels at the interim analysis and final analysis will be adjusted to maintain control of the overall type I error rate for multiple testing of PFS (O'Brien 1979).

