13.5.6 Safety Analyses

Safety will be assessed by clinical review of all relevant parameters including AEs, SAEs, laboratory values, vital signs, physical exam and ECG results. Unless specified otherwise, the safety analyses will be conducted for the safety population. An interim safety analysis is planned following the completion of Cycle 1 for the first 20 patients enrolled in the Phase 2 expansion phase and will utilize a Data Safety Monitoring Board.

Summary tables and listings will be provided for all reported Treatment Emergent Adverse Events (TEAEs), defined as AEs that start on or after the first administration of study treatment. The reported AE term will be assigned a standardized preferred term using the current version of the Medical Dictionary for Regulatory Activities (MedDRA).

TEAEs will be summarized based on the number and percentage of patients experiencing the event by MedDRA system organ class (SOC) and preferred term (PT). In the event a patient

experiences repeat episodes of the same AE, then the event with the highest severity grade and strongest causal relationship to study treatment will be used for purposes of incidence tabulations.

Tabular summaries will be provided for:

- all TEAEs
- TEAEs by relationship to study treatment and maximum severity grade
- TEAEs with action of study treatment delayed/interrupted or dose reduced
- TEAEs with action of study treatment discontinued
- SAEs

For the escalation phase, the observed DLT rate in each dose cohort will be calculated by the crude proportion of patients who experienced DLT with a 2-sided 95% exact binomial CI.

All deaths that occur on study (defined as during treatment or within 30 days of treatment discontinuation) will be reported in a patient listing, which will include the primary cause of death and the number of days between the date of the last dose of study drug and death.

Hematology and serum chemistries will be summarized in a descriptive manner by calculating the mean, standard deviation, median, and range as follows:

- baseline value
- minimum post baseline value
- maximum post baseline value
- average post baseline value
- last post baseline value

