5.2.2 Phase 2 Expansion Phase

The following assumptions are made:

- Patients in the control arm have true median PFS of 4 months
- Patients in the experimental arm have true median PFS of 7 months (under exponential distribution, true PFS hazard ratio of 0.57)
- Expected accrual duration will be 9 months and an additional 9 months of follow-up. The α type I error rate is set to 10% (1-sided)
- The β type II error rate is set to 20% (i.e. the power of the trial will be 80%)

Under these assumptions, 70 patients (35 per arm) will be enrolled in the trial, which is projected to result in 60 PFS failures, defined as documented disease progression by RECIST 1.1 or death due to any cause without documented disease progression beforehand, within approximately 18 months of the first patient randomized.

It is anticipated that the number of patients that drop out without PFS failure will be low (2-3%). Depending on the actual number of such dropouts, the number of patients accrued maybe increased by 6-10 patients to accommodate for a higher-than-expected number of dropouts.

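### Between-arm adverse events are reported only as crude percentages, which may overstate entinostat toxicity for events that keep accruing if treatment lasts longer in that arm

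*SAP*

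**What the plan says.** Protocol 13.5.6 states that "TEAEs will be summarized based on the number and percentage of patients experiencing the event", by system organ class and preferred term. SAP 10.9.2 repeats this ("Incidence of TEAE will be tabulated by SOC, PT for" several categories), and SAP 11.1 lists the tables: all TEAEs, by maximum grade, by relationship, by action taken, serious, and fatal. Neither document plans an exposure-adjusted rate, a time-to-first-event analysis, a cumulative incidence or a fixed-window AE table.

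Time at risk follows time on treatment. Protocol 6.4 and 9.9 continue treatment to unequivocal progression, unacceptable toxicity or another withdrawal criterion. Protocol 10.2.7 collects general AEs to 30 days after the last dose. Protocol 12.4 and 12.4.3 extend collection to 90 days for serious events, and to 90 days (or 30 days after new anticancer therapy, if earlier) for AEs of special interest (AESIs). The TEAE definition in SAP 6.10 has no end date.

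The design assumptions in SAP 5.2.2 are "Patients in the control arm have true median PFS of 4 months" and "Patients in the experimental arm have true median PFS of 7 months". SAP 10.7 summarises cycles, duration, cumulative dose and relative dose intensity by arm, but nothing links these to AE incidence.

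**The concern.** Safety and tolerability of the combination is a stated secondary objective, and the by-arm AE tables are the trial's only randomised safety evidence. A crude percentage counts everyone who has had the event by the time observation stops. When one arm is observed longer, the percentage mixes added toxicity with added time. If the trial succeeds on PFS, that mixing is likely to run against entinostat for every preferred term that accrues over time. A reader could see from the exposure table that durations differ, but could not adjust individual terms or grades from the planned tables.

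**Working it through.** **Inputs from the documents.** Median PFS 4 and 7 months; 35 patients per arm; 9 months of accrual plus 9 of follow-up (SAP 5.2.2). "Total information of 60 PFS failures" "is estimated to provide 80% power to detect a 43% reduction in the PFS failure hazard rate", "with 1-sided significance level of 0.1" (Protocol 13.1.2), with "1 planned interim analysis of PFS after 45 events (75% information") (Protocol 13.2). AE tail w = 30/30.4375 = 0.986 months.

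**Assumptions not in the documents.** Time on treatment equals PFS and is exponential; entry is uniform over 9 months; the AE hazard λ is constant and *identical* in the two arms, so there is no true difference.

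**1. The plan's own figure.** Fixed-design power = Φ(|ln 0.57|·√60/2 − 1.282) = Φ(2.177 − 1.282) = 0.815. With two Lan-DeMets O'Brien-Fleming looks at 45 and 60 events it is 0.804. The stated 80% is reproduced, so 7 versus 4 months is the alternative the trial is built on.

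**2. Time at risk.** The stopping hazards are μ = ln 2/4 = 0.1733 and ln 2/7 = 0.0990 per month.
- Without tail or cut-off: 1/μ = 5.77 and 10.10 months, ratio 1.75.
- Complete follow-up with the tail: 6.76 and 11.08 months, ratio 1.64.
- At 18 months: w + (1 − exp(−μ(F − w)))/μ, averaged over follow-up F from 9 to 18 months, gives 6.0 and 8.1 months, ratio 1.34.

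**3. Crude incidence.** With complete follow-up, P = 1 − exp(−λw)·μ/(μ + λ). For λ = 0.0358:
- control: 1 − 0.965 × 0.829 = 20.0%
- entinostat: 1 − 0.965 × 0.734 = 29.1%

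At 18 months, P is the average over F of ∫₀ᶠ λ·exp(−λt)·S(t) dt, where S(t) = 1 up to w and exp(−μ(t − w)) after it. In each column of the table λ is set to give the control value shown. The last column is √[(p₁(1 − p₁) + p₂(1 − p₂))/35], using the 18-month values.

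| Control | Entinostat, 18 months | Entinostat, complete follow-up | SE of difference |
|---|---|---|---|
| 5% | 6.6% | 7.9% | 5.6 points |
| 10% | 13.1% | 15.4% | 7.6 points |
| 20% | 25.8% | 29.1% | 10.0 points |
| 30% | 37.9% | 41.3% | 11.3 points |
| 40% | 49.3% | 52.3% | 11.8 points |
| 50% | 60.0% | 62.2% | 11.8 points |
| 80% | 86.8% | 86.9% | 8.9 points |

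At fixed hazards, the 18-month figures are 41% versus 51% for λ = 0.10 per month and 25% versus 31% for λ = 0.05.

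**4. Where the artefact goes away.**
- AE hazard confined to the first 21 days: 0 points. Confined to the first 42 days: at most 0.2 points.
- Extra stopping in the entinostat arm alone, at 18 months: 0.06 per month cuts the gap to 1.5 points (λ = 0.10) or 1.1 points (λ = 0.05). At 0.1733 − 0.0990 = 0.074 per month, exposure is equal and the gap is zero. Above that, the sign reverses.

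**5. What a rate would do.** Under a constant hazard, the 20% row at 18 months is 0.039 events per patient-month in both arms, ratio 1.00. For early-onset AEs with equal true risk, dividing by the longer exposure gives a ratio of 1/1.34 = 0.75, which falsely favours entinostat.

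**The case against.** A reader might infer that an effective entinostat arm is bound to show a false toxicity excess because it is treated 1.75 times as long. The documents do not support that, for four reasons.

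- The 1.75 is a ratio of median PFS, not of treatment time. Under Protocol 9.9 and 9.10, permanently stopping either drug ends all study treatment, so entinostat toxicity can shorten exposure in that arm. Treatment past first radiological progression is also possible (Protocol 10.3.2). Even if treatment time equals PFS, the tail and the cut-off reduce the ratio to 1.34.
- Early-onset AEs are unaffected.
- Some excess is likely to be real. Protocol 12.1.1 reports, from an earlier placebo-controlled breast cancer study, fatigue 48% versus 26%, nausea 40% versus 15% and neutropenia 30% versus 0%.
- At the 18-month cut-off the artefact is at most about one standard error for any single term.

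It is also fair to say that the AE tables are descriptive, that no formal safety stopping rule depends on them (Protocol 12.5), that exposure is tabulated and AE dates are listed, and that the data safety monitoring board's review after Cycle 1 compares nearly equal exposure.

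All of this limits the size and certainty of the problem without closing the gap. The bias is systematic across time-accruing terms, so sampling error on one row does not dispose of it. The protocol itself anticipates cumulative toxicity (6.1, 9.8). Since the direction of any exposure imbalance cannot be known in advance, the time-at-risk summary is better specified before unblinding.

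**Conclusion.** The gap is real: neither document relates AE incidence to time at risk. If entinostat achieves the assumed PFS effect and treatment time follows PFS, crude percentages may overstate its toxicity for AEs that keep accruing. The overstatement is about 2 to 10 points at the projected 18-month cut-off. It reaches about 12 points at the end-of-study safety analysis (SAP 5.4.2), which is close to complete follow-up. These sizes rest on exponential treatment times equal to PFS and an identical constant AE hazard. For AEs of the first one or two cycles the artefact is at most 0.2 points, and entinostat-only stopping of about 0.074 per month removes it. An observed excess would therefore be a mixture of real and duration-driven toxicity, and should not be called false as a whole. The primary PFS analysis is unaffected.

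The absence of any AESI summary from SAP 10.9.2 and 11.1 is a separate reporting omission. It is not evidence of exposure bias, but the same change can close it.

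**What to change.** In SAP 10.9.2 and 11.1, keep the crude tables and add two summaries by arm:

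1. Cumulative incidence of first event at fixed times, for example 3 and 6 months, stating how stopping treatment and death are handled.
2. First events per 100 patient-months at risk, with the rate difference and its confidence interval.

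Do this for all, Grade 3 or higher, serious, discontinuation-causing and special-interest AEs. Match each at-risk window to its collection period: 30 days after the last dose for general AEs; 90 days for serious events; 90 days, or 30 days after new anticancer therapy if earlier, for AESIs. A uniform 30-day window would drop serious and special-interest events collected after day 30. State the end of the TEAE window in SAP 6.10.

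Add a note that rates alone do not correct early-onset AEs, because they favour the longer-exposed arm (ratio about 0.75 in the case above); this is why both summaries are needed.

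The cost is a few more descriptive tables. AE start dates and first and last dose dates are already in the plan, so no new data are needed. The change should be made before unblinding.
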